2.2 Analysis sets

Full Analysis Set

The Full Analysis Set (FAS) comprises all patients to whom study treatment has been assigned and who received one dose of study treatment. Patients will be analyzed according to the treatment they have been assigned to.

Modified full analysis set

The modified Full Analysis Set (mFAS) comprises all patients of the FAS population who have PI3KCA mutation confirmed by a Novartis designated laboratory. The mFAS will be the primary population for the analysis of efficacy endpoints.

Per protocol set (PPS)

The Per-Protocol Set (PPS) consists of a subset of the patients in the mFAS who are compliant with requirements of the CSP.

The following list of protocol deviations will lead to exclusion of the patient from the Per-Protocol Set:

- *Patient has received prior treatment with PI3K inhibitors.*
- *Patient does not have a PIK3CA mutation that can be confirmed by a sample that can be provided to a Novartis designated laboratory (with >10% tumor tissue (15 slides minimum from a surgical specimen, or 20 slides minimum from a biopsy) OR Patient does not have a pathology report confirming PI3KCA mutation status by a CLIA certified laboratory (Using comparable PCR Tissue Mutation Assay) and cannot provide a tumor sample (either archival or newly obtained) collected after the most recent progression or recurrence for PIK3CA mutation for confirmation by a Novartis designated laboratory.*
- *Unconfirmed diagnosis of HER2-negative aBC as defined by a negative in situ hybridization test or IHC.*
- *Patient does not have a histologically and/or cytologically confirmed diagnosis of ER+ and/or PgR+ breast cancer by local laboratory.*
- *Patients are not: Diagnosed with aBC, with documented evidence of progression on or after CDK 4/6 inhibitor treatment. (Note: CDK 4/6 inhibitor has to be the last treatment regimen prior to study entry. Patients who received one prior chemotherapy for aBC (either in the adjuvant or metastatic setting) are allowed. Only one other prior anticancer therapy, e.g. tamoxifen, fulvestrant is allowed. The maximum number of*

prior therapies for aBC or mBC is limited to two. Patients must have recovered to grade 1 or better from any adverse events (except alopecia) related to previous therapy prior to study entry). AI treatment and received systemic chemotherapy or ET are as last treatment regimen in cohort C.

- *Patients do not have either: Measurable disease, at least one measurable lesion as per RECIST v1.1 criteria or If no measurable disease is present, then at least one predominantly lytic bone lesion must be present*
- *Patient has an ECOG performance status greater than 2 or ECOG missing*
- *Patient did not provide main study informed consent*
- *Patient enrolled in the wrong treatment cohort*
- *Patient who has been enrolled but not taken any dose of study drug*
- *Concurrent other anti-cancer therapy, or investigational therapy except palliative therapy, while on study treatment*
- *Concurrent treatment with prohibited drugs as per Protocol which puts patients under significant risk (please refer the Protocol section for Prohibited Medication)*

Safety Set

The **Safety set** includes all patients who received at least one dose of any component of the study treatment. Patients will be analyzed according to the study treatment actually received.

The actual treatment received corresponds to:

1. the assigned treatment if patients took at least one dose of that treatment.
2. the first treatment received if the assigned treatment was never received.

Safety Set in Extension Phase

The **Safety set in Extension Phase** includes all patients who received at least one dose of any component of the study treatment in Extension Phase. Patients will be analyzed according to the study treatment actually received.

The actual treatment received corresponds to:

1. the assigned treatment if patients took at least one dose of that treatment.
2. the first treatment received if the assigned treatment was never received.

Patient Classification:

Patients may be excluded from the analysis populations defined above based on the protocol deviations entered in the database and/or on specific patient classification rules defined in [Table 2-2.](#)

Table 2-2 Patient classification based on protocol deviations and non-PD criteria

Analysis set	Protocol deviations leading to exclusion	Non protocol deviation leading to exclusion
FAS	No written inform consent	No dose of study treatment received.
mFAS	No written inform consent	PI3KCA mutation not confirmed by a Novartis designated laboratory and no dose of study treatment received.
Safety set	No written inform consent	No dose of study treatment
Safety set in Extension Phase	No written inform consent	No dose of study treatment in Extension Phase
Per-protocol set	Any major protocol deviation as listed in definition of per protocol set (see definition of PP set)	Patient not evaluable for mFAS

Withdrawal of Informed Consent

Any data collected in the clinical database after a patients withdraws informed consent from all further participation in the trial, will not be included in the analysis. The date on which a patient withdraws full consent is recorded in the eCRF.

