5.2 Inclusion criteria

Patients eligible for inclusion in this study have to meet all of the following criteria:

Written informed consent must be obtained prior to any screening procedures.

- 1. Patient is an adult male or female ≥ 18 years old at the time of consent and has signed informed consent (ICF) before any trial related activities and according to local guidelines.
- 2. Males or females with advanced (locoregionally recurrent or metastatic) breast cancer not amenable to curative therapy.
- 3. Patient has a histologically and/or cytologically confirmed diagnosis of ER+ and/or PgR+ breast cancer by local laboratory.
- 4. Patient has a confirmed, HER2-negative aBC. HER2-negative defined as a negative in situ hybridization test or an immunohistochemistry (IHC) status of 0, 1+ or 2+. If IHC is 2+, a

- negative in situ hybridization (FISH, CISH, or SISH) test is required by local laboratory testing.
- 5. Patient has PIK3CA mutation confirmed by a Novartis designated laboratory, in which adequate formalin-fixed paraffin-embedded tissue sections with >10% tumor tissue must be provided. It is recommended to provide a tumor sample collected after the most recent progression or recurrence,

Or

- Patient has a pathology report confirming PIK3CA mutant status by a certified laboratory using a validated PIK3CA mutation assay (either from tissue or blood). It is also mandatory to provide a tumor sample (either archival or newly obtained) for PIK3CA mutation confirmation by a Novartis designated laboratory. It is recommended the tumor sample is collected after the most recent progression or recurrence.
- 6. In case of women, both premenopausal and postmenopausal patients are allowed to be included in this study; menopausal status is relevant for the requirement of goserelin or leuprolide to be used concomitantly with alpelisib in combination with fulvestrant or letrozole.
 - a. Patient is postmenopausal woman defined as either:
 - 1. Prior bilateral oophorectomy or
 - 2. Age \geq 60 or
 - 3. Age <60 and amenorrhea for 12 or more months (in the absence of chemotherapy, tamoxifen, toremifene, or ovarian suppression) and FSH and/or estradiol in the postmenopausal range per local normal range.
 - If patient is taking tamoxifen or toremifene and age <60, then FSH and plasma estradiol levels should be in post-menopausal range per local normal range.

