 - **Note**: For women using therapy-induced amenorrhea other than ovarian radiation, goserelin or leuprolide, serial measurements (per local guidelines) of FSH and/or estradiol are needed to ensure menopausal status.
 - b. Patient is premenopausal defined as either:
 - Patient had last menstrual period within the last 12 months OR
 - If on tamoxifen or toremifene with in the past 14 days, plasma estradiol and FSH must be in the premenopausal range per local normal range, OR
 - In case of therapy induced amenorrhea, plasma estradiol and/or FSH must be in the premenopausal range per local normal range
 - **Note:** Throughout this document, peri-menopausal and pre-menopausal status is grouped together and referred as "Premenopausal"
- 7. Patients must have documented evidence of tumor progression on or after
 - CDK 4/6 inhibitor treatment as last treatment regimen in cohorts A and B
 - AI treatment (either in adjuvant or metastatic setting) and received systemic chemotherapy or ET (monotherapy or combination except CDK 4/6i + AI) as last treatment regimen in cohort C: Note, upon completion of enrollment of Cohort B,

- No more than two (2) prior anti-cancer therapies for aBC. Each unique regimen or 'line' is defined as a single or combination of medications given for a new relapse/ recurrence. Maintenance therapies, where applicable, must be regarded as part of the main treatment.
- Received no more than one prior regimen of chemotherapy for the treatment of advanced/metastatic disease is permitted,
 - Note: Patients who received chemotherapy in (neo) adjuvant therapy for breast cancer are eligible.
- Recovered to grade 1 or better from any adverse events (except alopecia or other toxicities not considered a safety risk for the patient at investigator's discretion) related to previous anti-cancer therapy prior to study entry,
- 8. Patients must have either:

Measurable disease, i.e. at least one measurable lesion as per RECIST v1.1 criteria. (Tumor lesions previously irradiated or subjected to other locoregional therapy will only be considered measurable if disease progression at the treated site after completion of therapy is clearly documented),

or

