MRI	Magnetic Resonance Imaging
MUGA	Multiple Gated Acquisition
NCI	National Cancer Institute
CCI	CCI [REDACTED]
o.d.	Once Daily
ORR	Overall Response Rate
OS	Overall Survival
PD	Progressive Disease
PDI	Planned Dose Intensity
PFS	Progression-Free Survival
PFS2	Progression-Free Survival in next-line treatment
PgR	Progesterone Receptor
PI3K	Phosphatidylinositol-3-kinase
PIK3CA	Gene which encodes the p110alpha catalytic subunit of PI3K
PK	Pharmacokinetics
PPS	Per-Protocol Set
PR	Partial Response
PROS	Patient-reported Outcomes
PS	Performance Status
PSDS	Post-Study Drug Supply
PT	Preferred Term
qd	Quaque die / once a day
QoL	Quality of Life
QTcF	QT interval corrected by Fridericia method
RECIST	Response Evaluation Criteria in Solid Tumors
RDI	Relative Dose Intensity
SAE	Serious Adverse Event
SAP	Statistical Analysis Plan

SD	Stable Disease
SMQ	Standardized MedDRA Queries
SOC	System Organ Class
TA	Tumor Assessment
TEAE	Treatment-emergent Adverse Event
TFLs	Tables, Figures, Listings
TBL	Total Bilirubin
ULN	Upper Limit of Normal
WBC	White Blood Cell
WHO	World Health Organization
WoC	Withdrawal of Consent

1 Introduction

This statistical analysis plan (SAP) describes all planned analyses for the Clinical Study Report (CSR) of study CBYL719X2402, a phase II, multicenter, open-label, three-cohort, non-comparative study to assess the efficacy and safety of alpelisib plus fulvestrant or letrozole in patients with PIK3CA mutant, hormone receptor (HR) positive, HER2- negative advanced breast cancer (aBC), who have progressed on or after prior treatments.

The content of this SAP is based on protocol CBYL719X2402 V05. All decisions regarding final analysis, as defined in the SAP document, have been made prior to database lock.

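### The SAP's per-protocol exclusion list was only partly updated, and several items conflict with current inclusion criteria 5 and 7

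*SAP*

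**What the plan says.** SAP Amendment 4, section 2.2, describes the PPS as the part of the mFAS that is "compliant with requirements of the CSP". It then makes the list binding: "The following list of protocol deviations will lead to exclusion of the patient from the Per-Protocol Set". Table 2-2 of the SAP points back to that list, and Protocol 10.1.3 leaves the exclusion conditions to the data handling plan and the SAP. Section 1 of the SAP states its source: "The content of this SAP is based on protocol CBYL719X2402 V05".

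Two items of the list matter here. The PIK3CA item asks for tissue ("15 slides minimum from a surgical specimen, or 20 slides minimum from a biopsy") or, for local reports, a CLIA laboratory with a PCR tissue assay and a sample taken after the latest progression. The prior-therapy item says "CDK 4/6 inhibitor has to be the last treatment regimen prior to study entry", adds limits on earlier treatment and toxicity, and ends with an ungrammatical sentence about Cohort C.

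Protocol 5.2, criterion 5, gives no slide count: "adequate formalin-fixed paraffin-embedded tissue sections with >10% tumor tissue must be provided". On timing it says only "It is recommended the tumor sample is collected after the most recent progression or recurrence". Criterion 7 keeps the CDK4/6 condition for Cohorts A and B and sets a different one for Cohort C: "AI treatment (either in adjuvant or metastatic setting) and received systemic chemotherapy or ET (monotherapy or combination except CDK 4/6i + AI) as last treatment".

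**The concern.** A per-protocol analysis is informative when the patients it removes really departed from the protocol. If the list removes patients who met every current criterion, the PPS differs from the mFAS by prior treatment, residual toxicity or type of laboratory report. Agreement or disagreement between the two results then says little about robustness to deviations. If the analysts instead follow the current criteria and disregard the text, the PPS they use is no longer the pre-specified one.

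**Working it through.** **The plan's own figure.** Inputs are n = 112 per cohort, a cut-off of 44, one-sided 2.5% and a true rate of 0.45 (Protocol 10.4.2 and 10.8), with a null rate of 0.30 (Protocol summary, Data analysis).

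- Type I error = P(X ≥ 44 | 112, 0.30) = 0.0225.
- Power = P(X ≥ 44 | 112, 0.45) = 0.9055, which reproduces the stated minimum of 90%.
- The exact 95% lower bound is 29.4% at 43/112 and 30.2% at 44/112, so 44 is the right cut-off.

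None of this involves the PPS.

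**The two texts side by side.**

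| Item | SAP 2.2 (PPS list) | Protocol 5.2, criteria 5 and 7 |
|---|---|---|
| Recovery from earlier toxicity | Alopecia is the only exemption | Alopecia, plus toxicities the investigator judges not to be a safety risk |
| Chemotherapy | One allowed, adjuvant use counted | One regimen for advanced disease; (neo)adjuvant chemotherapy does not bar entry |
| Other earlier therapy | One other, setting not given (as well as at most two for advanced disease) | At most two lines, counted for advanced disease only |
| Last regimen | CDK4/6 inhibitor, cohort not stated; then a Cohort C sentence | CDK4/6 inhibitor in A and B; chemotherapy or endocrine therapy in C, but not CDK4/6 inhibitor plus AI |
| Local PIK3CA report | CLIA laboratory, PCR tissue assay | Certified laboratory, validated assay on tissue or blood |
| Sample after last progression | Written as a condition | Recommended |
| Slide count | 15 or 20 | None in the criterion |

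**Who would fail the list but meet the criterion.** Three hypothetical patients show it:

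1. A patient with a residual grade 2 toxicity that the investigator accepted under criterion 7.
2. A Cohort A patient with adjuvant chemotherapy, one chemotherapy regimen for advanced disease, then a CDK4/6 inhibitor plus AI. That is two lines and one chemotherapy for advanced disease, so criterion 7 is met; the SAP counts two chemotherapies.
3. A patient who took two successive adjuvant endocrine agents before a CDK4/6 inhibitor plus AI. That is one line for advanced disease, but two other earlier therapies under the SAP.

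**Last regimen.** The Cohort C sentence is not joined to the exclusion by any connective, so how it modifies the CDK4/6 rule is left to the programmer. It also drops the exception for CDK4/6 inhibitor plus AI, which makes the list looser than criterion 7 at that point. The separate exclusion for enrolment in the wrong cohort would probably catch such a patient.

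**PIK3CA item.** It has two limbs joined by OR. The second applies only if the patient lacks a qualifying report **and** cannot supply a post-progression sample. A patient with a CLIA report is therefore not caught by it, however old the tissue is. All PPS patients are in the mFAS and already have central confirmation. If the OR means failing both routes, almost nobody is affected. Read literally, it reaches centrally confirmed patients who have no qualifying report and only older tissue.

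**Size.** The documents do not say how many patients meet any of these descriptions. As illustration only, assume a share of a 112-patient cohort is dropped and the rate in those left is still 0.45. The cut-off is the smallest count whose exact 95% lower bound exceeds 0.30.

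| Assumed share dropped | n | Cut-off | Power at 0.45 |
|---|---|---|---|
| 5% | 106 | 42 | 88.7% |
| 10% | 101 | 40 | 88.3% |
| 20% | 90 | 37 | 80.1% |

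The lost precision is modest. The main problem is which patients are removed.

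**The case against.** The case against rests on five points.

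- **Deviations drive exclusion.** The list is one of protocol deviations, and SAP 2.2 applies it through deviations entered in the database. A patient who meets criteria 5 and 7 should have none recorded. This stands as a limit on size, and the data handling plan is not available to check. It does not cure the text, because the SAP is where the set is defined.
- **Cohort C.** A reader might infer that all Cohort C patients whose last regimen lacked a CDK4/6 inhibitor are dropped. The closing sentence of the same item shows that this was not intended, and the SAP history records a PPS update in the revision that added Cohort C. What stands is ambiguity, not a rule against Cohort C.
- **Tissue.** A reader might infer that every local-report patient with older archival tissue is excluded, or that the slide minimum is obsolete. The first fails on the conjunction shown above, and the SAP item itself accepts archival samples. The second is not shown: the Amendment 1 log says the slide requirement was only moved out of the criteria, and Protocol 7.1.1 sends tissue requirements to the laboratory manual. Nor do the documents support tissue age as a factor linked to outcome.
- **Toxicity.** The protocol summary gives alopecia alone, and exclusion criterion 15 has an alopecia-only exemption for drugs with overlapping toxicities. So some patients admitted under criterion 7 might fail elsewhere. The mismatch with criterion 7 remains.
- **Role.** The PPS repeat is optional in Protocol 10.4.4. SAP 2.5.4 also makes it conditional on the mFAS hypothesis being met. This stands in full.

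Following V05 rather than V06 is no explanation: the Amendment 6 change list names nothing in section 5.

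**Conclusion.** The point holds in this limited form: the PPS list contradicts the criteria it is meant to enforce. The firmest conflicts are the limits on earlier chemotherapy and other therapy, the toxicity exemption in criterion 7 and the last-regimen wording. The laboratory and sample-timing conflicts are real but probably touch few patients, because the PPS sits inside the centrally confirmed mFAS.

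Some compliant patients would be excluded if the list is coded as written. Their number is unknown and may be small; the conclusion assumes literal application. A reader might go further and infer that the primary result is at risk. It is not: the primary analysis uses the mFAS, the FAS repeat is planned regardless of the PPS, and the cut-off and power stand. The correction is still worth making, because the rule is wrong as written and cheap to repair.

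**What to change.** Restate the two items in SAP 2.2 from current criteria 5 and 7:

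- **Last regimen, by cohort.** A: CDK4/6 inhibitor plus AI. B: CDK4/6 inhibitor plus fulvestrant. C: progression on or after an AI, with chemotherapy or endocrine therapy last, excluding CDK4/6 inhibitor plus AI; CDK4/6 inhibitor plus fulvestrant is admitted once Cohort B has closed.
- **Earlier therapy.** Apply the chemotherapy limit and the two-line limit to advanced disease only, and say that (neo)adjuvant chemotherapy does not exclude.
- **Toxicity.** Use the full exemption in criterion 7, and reconcile it with exclusion criterion 15 and the protocol summary.
- **PIK3CA.** Accept a certified laboratory with a validated tissue or blood assay, and make the post-progression sample non-exclusionary. Keep the slide minimum as an exclusion only if it is confirmed as a current protocol requirement.
- **Deviation codes.** Align them with the new wording and report the number excluded under each item, by cohort.

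The cost is SAP wording and code mapping. No new data are needed. If a PPS repeat has already been run on the present list, show it beside the corrected one.

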10.1 Analysis sets

10.1.1 Full analysis Set

The Full Analysis Set (FAS) comprises all patients to whom study treatment has been assigned and who received one dose of study treatment. Patients will be analyzed according to the treatment they have been assigned to.

Modified full analysis set

The modified Full Analysis Set (mFAS) comprises all patients of the FAS population who have PIK3CA mutation confirmed by a Novartis designated laboratory. mFAS will be the primary population for the analysis of efficacy endpoints.

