2.5.1 Primary endpoint

The primary efficacy endpoint is the proportion of patients who are alive without disease progression at 6 months based on local investigator assessment using RECIST v1.1 in each cohort.

The mFAS will be used for the primary efficacy analysis.

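### The mFAS row of SAP Table 2-2 joins its two exclusion grounds with 'and', where the mFAS definition requires 'or'

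*SAP*

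**What the plan says.** SAP Amendment 4, section 2.2, defines the analysis sets in text and then restates them as exclusion rules in Table 2-2.

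- **FAS definition (SAP 2.2):** it "comprises all patients to whom study treatment has been assigned and who received one dose of study treatment".
- **mFAS definition (SAP 2.2):** it "comprises all patients of the FAS population who have PI3KCA mutation confirmed by a Novartis designated laboratory". Protocol 10.1.1 has the same definition: the set "comprises all patients of the FAS population who have PIK3CA mutation confirmed by a Novartis designated laboratory".
- **FAS row of Table 2-2:** the non-deviation exclusion ground is "No dose of study treatment received".
- **mFAS row of Table 2-2:** the non-deviation exclusion ground is "PI3KCA mutation not confirmed by a Novartis designated laboratory and no dose of study treatment received".

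The paragraph introducing the table says patients may be excluded from the sets already defined, on the basis of recorded protocol deviations "and/or on specific patient classification rules defined in" that table.

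The mFAS is the main efficacy set. SAP 2.5.1 states: "The mFAS will be used for the primary efficacy analysis". Protocol 10.1.1 agrees: "mFAS will be the primary population for the analysis of efficacy endpoints". SAP 2.7.1 and 2.2.1 also use it for the secondary efficacy endpoints and the subgroups. SAP 2.5.4 plans a supportive repeat of the primary analysis on the FAS.

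**The concern.** The definition has two requirements, dosed and centrally confirmed. An exclusion rule that restates it must remove anyone who fails either one. The mFAS row removes only those who fail both, so the text and the table in one SAP section select different primary populations.

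The affected patients are foreseen in the design. Protocol 5.2 (criterion 5) and 7.1.2 allow entry on a certified laboratory's report, with tissue still to be sent for central confirmation. Protocol 7.1.5.1 says that patients who entered on a local report and were not confirmed, or whose results disagreed, are to be replaced. Replacement makes sense only if they leave the primary population.

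If the row were applied as written, these patients would enter both numerator and denominator of the primary proportion. The planned FAS analysis could then no longer show whether the result depends on them.

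**Working it through.** **1. The plan's own design figures.** Inputs: N = 112 per cohort, success if at least 44 patients are alive without progression, one-sided 2.5% level, power of at least 90% at p = 0.45 (SAP 2.5.2 and 3.1). The null value p0 = 0.30 comes from the data analysis row of the protocol summary, because the SAP value is redacted.

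- Exact type I error: P(X ≥ 44 | 112, 0.30) = 0.0225.
- Exact power: P(X ≥ 44 | 112, 0.45) = 0.9055.
- Clopper-Pearson lower limit, the 0.025 quantile of Beta(k, n − k + 1): 44/112 gives 30.19% and 43/112 gives 29.36%. So 44 is the correct minimum.

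These figures reproduce and do not depend on Table 2-2.

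**2. The logic of the row.** By definition, a patient is in the mFAS if confirmed AND dosed. The negation is unconfirmed OR undosed. The table has unconfirmed AND undosed.

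| Patient | By definition | mFAS row read literally | Literal row, after restriction to the FAS |
|---|---|---|---|
| Confirmed, dosed | in | in | in |
| Confirmed, not dosed | out | in | out |
| Unconfirmed, dosed | **out** | **in** | **in** |
| Unconfirmed, not dosed | out | out | out |

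Once the FAS restriction applies, one cell disagrees: unconfirmed and dosed, the group the mFAS exists to remove. Everyone in the FAS has been dosed, so the literal ground removes nobody from it and mFAS = FAS. With 'or', all four cells match the definition.

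**3. Illustration only.** The number m of dosed, unconfirmed patients in a cohort is not in the documents, and neither is their success rate. Assume 112 confirmed patients with p = 0.45, add m unconfirmed patients with rate q, reset the success threshold for the larger N, and sum two independent binomials.

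| m | N | Threshold | Power, q = 0.20 | q = 0.30 | q = 0.45 |
|---|---|---|---|---|---|
| 0 | 112 | 44 | 0.906 | 0.906 | 0.906 |
| 5 | 117 | 46 | 0.866 | 0.884 | 0.909 |
| 10 | 122 | 48 | 0.817 | 0.860 | 0.912 |
| 20 | 132 | 51 | 0.758 | 0.852 | 0.941 |

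The direction depends on q: a low rate dilutes the result, and a rate equal to that of confirmed patients slightly raises power through the larger N.

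**The case against.** The strongest reply is that the mFAS is fixed by an inclusion definition, given consistently in the protocol summary, protocol 10.1.1 and SAP 2.2. A dosed, unconfirmed patient fails it and never enters the set. Table 2-2 only removes patients from sets already defined and cannot add anyone. The literal reading also defeats itself: it would make the mFAS identical to the FAS, although the SAP plans separate analyses on each. The cell can be read as a loose list of two grounds, so 'and' is most likely a drafting slip. This reply stands as far as it goes. It shows what was intended, but the row still misstates the rule, and the SAP presents the table as one to be applied.

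Four stronger readings are tempting and are not supported.

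- **That unconfirmed patients are in the primary population.** The documents do not show this. It depends on how the set was programmed.
- **That up to 44 patients are affected**, from 380 enrolled minus 3 × 112 = 336. The plan asks for at least 112 per cohort and about 340 in total, so 336 is not a cap on confirmed patients and the excess may be ordinary over-enrolment. Nor is 44 an upper bound, since a cohort could have fewer than 112 confirmed. The protocol glossary ties enrolment to consent, so the 380 may include undosed patients. The figure also pools three cohorts that are tested separately.
- **That the primary conclusion would flip.** At exactly 44/112, adding 3 successes in 10 gives 47/122 with a lower limit of 29.9%, which fails. Adding 4 in 10 gives 48/122 with 30.6%, which passes. With ten added patients, a success can be lost only if confirmed successes number 44 to 47; from 48 upwards, even 0 of 10 still passes. The design rate implies 112 × 0.45 = 50.4 successes. This is a selected boundary case.
- **That the error carries fully into the PPS.** The PPS row does refer to the mFAS, but the PPS has its own deviation on mutation confirmation, so the carry-over is at most partial.

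Timing also matters. Enrolment was complete by 14 December 2020 and each cohort's primary analysis was due six months after its last patient started, so roughly by mid-2021. Amendment 4 is dated 24 March 2022. Whether earlier SAP versions had the same row cannot be seen from these documents.

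**Conclusion.** The mFAS row of Table 2-2 is wrong as written: it contradicts the definition of the primary efficacy population in the same section and in the protocol. That holds on the text and needs no assumption.

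The consequence is conditional. Only if the row is programmed literally do dosed patients without central confirmation stay in the primary population, with the mFAS equal to the FAS and the supportive FAS analysis duplicating the primary one. How many patients this would involve is not stated, so no effect on the observed proportion can be given, and the power table rests entirely on assumed numbers. The stated sample size, the 44/112 threshold and the stated power are unaffected. It is worth correcting because it concerns the primary analysis set and the correction is unambiguous, not because harm has been shown.

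**What to change.** In the mFAS row of Table 2-2, replace 'and' with 'or'. An equivalent and safer wording is: *not in the FAS, or PIK3CA mutation unconfirmed by the designated laboratory*. This ties the row to the FAS and avoids restating the dosing condition.

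For analyses already run, check that the mFAS flag was derived from the definition (dosed and centrally confirmed) and say so in the study report, with the number of FAS patients left out of the mFAS in each cohort. The SAP already plans counts of patients per analysis set by cohort, so this adds almost nothing.

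The cost is one word in the SAP and one check of the derivation code. No design figure, data collection or analysis method changes.
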